#### 14.5.3. Publication

All publication or presentation rights for the findings of the clinical investigation under this protocol shall be governed by the appropriate terms of the Clinical Research Agreement between the investigational site and the Sponsor.

# 15. QUALITY CONTROL AND QUALITY ASSURANCE

The study will be monitored and managed in accordance with ICH-GCP.

To ensure compliance with GCP and all applicable regulatory requirements, the Sponsor or its representatives may conduct a quality assurance audit. Regulatory agencies may also conduct a regulatory inspection of this study. Such audits/inspections can occur at any time during or after completion of the study. If an audit or inspection occurs, the Investigator and institution agree to allow the auditor/inspector direct access to all relevant documents and to allocate his/her time and the time of his/her staff to the auditor/inspector to discuss findings and any relevant issues.

## 16. DATA HANDLING AND RECORDKEEPING

## 16.1. Case Report Forms

All required study data must be recorded on the electronic CRF provided by the Sponsor or its representatives. The data recorded onto the electronic CRF is derived from the source documents. The Investigator shall ensure that all data in the electronic CRF is accurate and consistent with the source documents or that any discrepancies of the electronic CRF with source documents are explained (ICH-GCP 4.9.2).

Electronic case report forms will be accessed by the study center for collection of all study data, and a copy of the electronic CRF will be provided to the site for the Investigator files. For each subject who is randomized, the electronic CRF must be completed by site staff and must be signed electronically by the Principal Investigator in a timely fashion after data collection. If a subject withdraws from the study, the electronic CRFs should be promptly completed and the reason for withdrawal must be noted. If a subject is withdrawn from the study because of a drug-related toxicity, thorough efforts should be made to clearly document the outcome.

# 16.2. Retention/Inspection of Records

The Investigator must maintain adequate and accurate records to enable the conduct of the study to be fully documented and the study data to be subsequently verified.

Records of drug receipt and disposition, electronic file of CRFs, source documents, reports of this investigation and other study documentation must be maintained by the Investigator for a period of at least two years for US sites and 25 years for Canadian sites following the date on

which the investigational drug is approved by FDA or other applicable regulatory agency for marketing for the purposes that were the subject of the clinical investigations. If no application is to be filed, records must be retained until two years for US sites and 25 years for Canadian sites following the date that the study is discontinued, and the FDA or other applicable regulatory agency is notified. If the application is not approved by the FDA or other applicable regulatory agency for such indication, records must be retained for two years for US sites and 25 years for Canadian sites after notification by the Sponsor of the FDA or other applicable regulatory agency decision. The records must be available for copying and inspection if requested by regulatory authorities.

Galera Therapeutics, Inc.

Version: Amendment 4

The Sponsor should be notified in writing at least 30 days prior to the disposal or transfer to another location or party of any study records related to this protocol.

### 18. APPENDICES

Galera Therapeutics, Inc. Version: Amendment 4

### APPENDIX 1. SCHEDULE OF ASSESSMENTS

**Table 6: Schedule of Assessments** 

Assessments	Screening	Treatment						Follow-up						
					Post-IMRT	Long-term Follow-up								
											OM Follow-up			
	≤28 days	Wk 1		Wk 2	Wk 3	Wk 4	Wk 5	Wk 6	Wk 7	Last Day	Post-IMRT	Months 3,	Months	Months 16, 20,
	of IMRT Day 1	Baseline (IMRT Day 1)	Days 2-7	Days 8-14	Days 15-21	Days 22-28	Days 29-35	Days 36-42	Days 43-49	of IMRT or Early Term 	Wks 1 & 2 (±2 D) 	6, 9, & 12 Post- IMRT (±30 D)	3 & 12 Post- IMRT (±30 D)	24 Post-IMRT (±30 D)
Informed consent	X													
Inclusion/exclusion criteria 	X	X												
Dental exam/IMRT clearance	X													
Medical and HNC histories 	X													
Record tobacco use	X	X		X	X	X	X	X	X					
Complete physical exam 	X									X				
Height	X													
Weight	X	X		X	X	X	X	X	X	X				
Symptom-directed PE						X								
Vital signs, ECOG 	X	X				X			X	X				
Record BSA 		X		X	X	X	X	X	X					
Tumor imaging 	X												X	
Clinical tumor assessment 										X		X	X	
Concomitant medications 	X	X	Weeko	days						X	X			
Adverse Events 	X	X	Weeko	days						X	X			
ECG (12-lead) 	X													
OM assessment 	X	X	X	Twice-	weekly				X	X	X			
Blood draw: Serum pregnancy test 	X													
Blood draw: Lab safety tests 	X	X	X	X	X	X	X	X	X	X 				
Blood draw: Serum cotinine 		X				X				X				
Blood draw: PK 		X	X			X								
Blood draw: Cytokines 	X	X		X		X		X		X				
Blood draw: RNA 	X									X				
Dosing GC4419/Placebo 		X Weekdays when IMRT is given X												
BUN, creatinine, and weight								X						
Survival Status 			1									X	X	X

BSA = body surface area; ECG = electrocardiogram; ECOG = Eastern Cooperative Oncology Group; HNC = head and neck cancer, IMRT = intensity-modulated radiation therapy; OM = oral mucositis; PE = physical examination; PK = pharmacokinetics

#### Table footnotes

-  If a subject ends study participation early and/or withdraws consent after randomization, all last day of IMRT procedures should be completed.
-  The Post-IMRT Weeks 1 and 2 Follow-up Visits will be scheduled based on the last day of IMRT. All subjects will be seen at  $7 \pm 2$  calendar days from the last day of IMRT and  $14 \pm 2$  calendar days from the last day of IMRT.

Galera Therapeutics, Inc.

Version: Amendment 4

-  See protocol Sections 7.1 and 7.2.
-  The HNC history should include tumor HPV status, staging (AJCC 8th Edition) information, prior treatments, and confirmation of histopathological diagnosis of SCC. Medical conditions and illnesses that have occurred since the subject signed the ICF up until the date of randomization should be recorded as medical history. Medical history also includes tobacco and alcohol use history.
-  At the Screening and Last Day of IMRT Visits, a complete physical examination will be conducted.
-  Vital signs (temperature, systolic and diastolic blood pressures, heart rate, and respiration rate), and ECOG will be obtained and recorded at the Screening and Baseline Visits, once during Weeks 4 and 7, and at the Last Day of IMRT Visit. All vital signs should be measured following 2 minutes of rest in the sitting position. On Day 1 (Baseline) and Day 22, blood pressure must be measured at the following times: 1) within 30 minutes prior to the pre-GC4419/Placebo PK draw, and 2) after GC4419/Placebo infusion, prior to standing and prior to the End of GC4419/Placebo Infusion PK draw.
-  For subjects receiving tri-weekly cisplatin, body surface area (BSA) will be recorded to confirm cisplatin dosing at the Baseline Visit and once during Weeks 4 and 7. For subjects receiving weekly cisplatin, BSA will be recorded to confirm cisplatin dosing at the Baseline Visit and once per week until chemotherapy is completed.
- Radiographic imaging must be performed within 60 days prior to the first day of IMRT for definitively treated subjects. Imaging can occur prior to the 60-day window for post-operatively treated subjects. Pre-surgical imaging should be captured if available; post-surgical imaging will be accepted otherwise. Imaging must occur at Month 12 post-IMRT for all subjects. Subjects treated definitively (as opposed to post-operatively) will also undergo imaging at Month 3 post-IMRT to assess tumor response/clearance to the degree possible. Radiographic imaging is highly recommended at any post-IMRT follow-up visit at which disease progression is suspected by the treating physician. If radiographic imaging is performed, both local/regional recurrence and distant metastases should be evaluated.
-  At the Last Day of IMRT Visit, a clinical tumor assessment will be conducted. A head/neck/oral exam is sufficient on the Last day of IMRT if disease progression is not suspected. If disease progression is suspected, a laryngopharyngoscopy should be conducted. At Months 3, 6, 9, and 12 a laryngopharyngoscopy (mirror and/or fiberoptic and/or direct procedure) is required to evaluate local/regional or distant progression. However, if local/regional progression or recurrence has already been discovered at a previous visit, a laryngopharyngoscopy is no longer required at future visits. If distant progression is discovered at a previous visit, a laryngopharyngoscopy is still required at subsequent visits to assess the subject for local/regional progression/recurrence. A head/neck/oral exam should always be conducted at Months 3, 6, 9, and 12 post-IMRT.
- All concomitant therapies (e.g., prescription and over-the-counter medications) taken by subjects on or after the date of randomization through 30 days following the last dose of GC4419/Placebo, IMRT or cisplatin (i.e. whichever occurs last) will be collected in the CRF. Any concomitant therapies used to treat any serious or related adverse event will be recorded in the CRF.
- AEs and SAEs with onset dates on or after the date of randomization through 30 days following the last dose of GC4419/Placebo, IMRT or cisplatin (i.e. whichever occurs last) will be recorded on the CRF. All subjects with SAEs will be followed until the events resolve, stabilize, become chronic, the subject completes the study, or the subject is lost to follow-up.
- Ventricular rate and P-R, QRS, QT, and QTc intervals will be assessed and recorded at Screening.

Galera Therapeutics, Inc. Version: Amendment 4

- $^{13}$ All OM assessments must be performed by trained evaluators. The extent of the subject's OM will be scored using the WHO OM toxicity scale. OM assessments will be completed at the Screening Visit, at the Baseline Visit, and twice weekly (no less than two days apart) within each 5-day IMRT period. For Week 1, the first OM assessment will occur at the Baseline Visit and one additional OM assessment must occur at least two days later during the week. The extent of the subject's OM will be scored using the WHO OM toxicity scale. All subjects will be seen at  $7 \pm 2$  calendar days from the last day of IMRT and  $14 \pm 2$  calendar days from the last day of IMRT.
- For a woman of childbearing potential, serum pregnancy test must be performed at the Screening Visit.
- Clinical laboratory measurements will be conducted at the Screening Visit, twice during Week 1 (once at the Baseline Visit and again on Day 3, 4 or 5), and once weekly from Week 2 through the last day of IMRT. Clinical laboratory measurements at these visits will include the hematology profile (hemoglobin, hematocrit, red blood cell count, white blood cell count with differential, and platelet count. Differential to include total neutrophils, lymphocytes, monocytes, eosinophils, and basophils) and chemistry profile (glucose, BUN, creatinine, sodium, potassium, calcium, albumin, total protein, total bilirubin, direct bilirubin, alkaline phosphatase, ALT (SGPT), AST (SGOT), chloride, phosphate, bicarbonate, magnesium).
-  If safety labs have already been drawn during the study week in which the last day of IMRT or early termination visit falls, then lab safety tests (chemistry and hematology profiles) do not need to be conducted on the last day of IMRT or at the early termination visit. If safety labs have not been drawn during the current study week at the time of the early termination visit or on the last day of IMRT, then safety labs should be drawn on that day. Safety labs only need to be drawn once per study week after Week 1.
- Blood samples will be collected for serum cotinine test at Baseline (Day 1), once during Week 4, and on the Last Day of IMRT.
- Blood samples will be collected for GC4419 pharmacokinetic (PK) measurements at Baseline (Day 1), Day 2, and Day 22. See Table 4 for additional information.
- For cytokine analysis, blood samples will be collected at the Screening Visit (within 28 days of IMRT start but at least 72 hours prior to Baseline), at the Baseline Visit, Week 2 OM Visit 2, Week 4 OM Visit 2, Week 6 OM Visit 2, and at the Last Day of IMRT Visit. Whenever possible, blood draws for cytokine analysis should be conducted at OM Visit 2 for each protocol-specified week; however, if blood draws must be taken on another day within a given week, it will not be considered a protocol deviation.
- If the subject consents separately, blood samples will be collected at the Screening Visit (within 28 days of IMRT start but at least 72 hours prior to Baseline) and at the Last Day of IMRT Visit for the assessment of gene expression patterns prior to receiving the first dose of GC4419 and upon completion of GC4419 doses.
- GC4419/Placebo will be administered up to 35 times: weekly, Monday through Friday, beginning at Baseline (IMRT Day 1) and continuing through the 35th dose. IMRT must begin no longer than 60 min following the end of the GC4419/Placebo infusion. If IMRT is not received on any given day due to a treatment break or unforeseen circumstances, GC4419/Placebo should not be administered on that day. Subjects should resume GC4419/Placebo administration when IMRT resumes. If GC4419/Placebo was already administered on a given day and IMRT is not administered due to unforeseen circumstances, that day's GC4419/Placebo dose will still count as one of the 35 doses.
- Subjects will be followed for survival for two years. The subject's survival status will be assessed at the following time points: Every 3 months, ± 30 days, throughout the 1st year post-IMRT (Months 3, 6, 9, and 12), and Every 4 months, ± 30 days, throughout the 2nd year post-IMRT (Months 16, 20, and 24).

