## 7.1. Subject Inclusion Criteria

Patients are required to meet the following inclusion criteria before entering the study:

1. Pathologically-confirmed diagnosis of squamous cell carcinoma of the head and neck, defined as SCC of the oral cavity or oropharynx that will be treated with cisplatin plus concurrent IMRT.

Note: Patients with unknown primary tumors whose treatment plan matches the requirements specified in Inclusion Criteria #2 and #3 below are eligible for the study.

2. Treatment plan to receive a continuous course of IMRT delivered as single daily fractions of 2.0 to 2.2 Gy with a cumulative radiation dose of 60-72 Gy. Planned radiation treatment fields must include at least two oral sites (left and right buccal mucosa, floor of mouth, left and right ventral/lateral tongue, soft palate) that are each planned to receive a total of ≥ 50 Gy. Patients who have had prior surgery are eligible, provided they have fully recovered from surgery, and patients who may have surgery in the future are eligible.

Note: Unavoidable doses of at least 50 Gy, to include entrance, exit, and scatter doses, still constitute planned radiation.

3. Treatment plan to receive standard cisplatin monotherapy administered either every three weeks (100 mg/m² for 3 doses) or weekly (40 mg/m² for 6-7 doses). The decision on which cisplatin regimen to use in combination with IMRT and GC4419/Placebo will be at the discretion of the Investigator.

Galera Therapeutics, Inc.

Version: Amendment 4

- 4. Age 18 years or older
- 5. Eastern Cooperative Oncology Group (ECOG) performance status  $\leq 2$
- 6. Adequate hematologic function as indicated by:
  - Absolute neutrophil counts (ANC)  $\geq 1,500/\text{mm}^3$
  - Hemoglobin (Hgb)  $\geq$  9.0 g/dL
  - Platelet count  $\geq 100,000/\text{mm}^3$
- 7. Adequate renal and liver function as indicated by:
  - Serum creatinine acceptable for treatment with cisplatin per institutional guidelines
  - Total bilirubin ≤  $1.5 \times \text{upper-normal limit (ULN)}$
  - Aspartate aminotransferase (AST) and alanine aminotransferase (ALT)  $\leq$  2.5  $\times$  ULN
  - Alkaline phosphatase  $\leq 2.5 \times ULN$
- 8. Serum pregnancy test negative for females of childbearing potential
- 9. Males and females must agree to use effective contraception starting prior to the first day of treatment and continuing after the last dose of GC4419/Placebo for 30 days (females) or 90 days (males)
- 10. Properly obtained written informed consent

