## 7.2. Subject Exclusion Criteria

Patients will be excluded if they meet any of the following exclusion criteria:

- 1. Tumor of the lips, larynx, hypopharynx, nasopharynx, sinuses, or salivary glands
- 2. M1 disease (distant metastasis)
- 3. Prior radiotherapy to the region of the study cancer or adjacent anatomical sites or more than 25% of total body marrow-bearing area (potentially interfering with chemotolerance)
- 4. Prior induction chemotherapy for current HNC or any prior immunotherapy
- 5. Receiving any approved or investigational anti-cancer agent other than those provided for in this study
- 6. Concurrent participation in another interventional clinical study or use of another investigational agent within 30 days of first dose of GC4419/Placebo

Note: Patients who are participating in non-interventional clinical studies (e.g., QOL, imaging, observational, follow-up studies, etc.) are eligible, regardless of the timing of participation.

7. Inability to eat soft solid food at baseline for reasons other than mouth soreness after surgery or dental procedures

Galera Therapeutics, Inc.

Version: Amendment 4

8. Complete reliance on parenteral or gastrointestinal tube-delivered nutrition at baseline

Note: Patients who have gastrostomy tubes prophylactically placed are eligible. Patients receiving supplemental nutrition through a gastrostomy tube at baseline may be eligible depending on diet.

- 9. Malignant tumors other than HNC within the last 5 years, unless treated definitively and with low risk of recurrence in the judgment of the treating Investigator
- 10. Active infectious disease excluding oral candidiasis
- 11. Presence of oral mucositis at baseline. Subjects with mouth or throat pain solely due to post-operative effects are eligible, however.
- 12. Known history of human immunodeficiency virus (HIV) or history of active hepatitis B/C (patients who have been vaccinated for hepatitis B and do not have a history of infection are eligible)
- 13. Female patients who are pregnant or breastfeeding
- 14. Known allergies or intolerance to cisplatin and similar platinum-containing compounds
- 15. Requirement for concurrent treatment with nitrates or other drugs that may, in the judgment of the treating Investigator, create a risk for a precipitous decrease in blood pressure.

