## 10.4. Pharmacokinetic (PK) Measurements

# 10.4.1. Pharmacokinetic (PK) Measurements of GC4419

PK sampling will be sought from all subjects for GC4419.

Plasma samples for GC4419 PK measurements will be collected in two cycles: Study Days 1 and 2, and on Study Day 22. On Study Days 1 and 22, four samples will be drawn as follows:

The first sample will be drawn prior to GC4419/Placebo administration.

The second sample will be drawn within 10 minutes after the end of GC4419/Placebo infusion.

The third sample will be drawn within 10 minutes after the end of IMRT.

The fourth and final sample will be drawn between 60 and 180 minutes after the end of GC4419/Placebo infusion.

On Study Day 2 only one PK sample will be drawn. This sample should be drawn prior to the GC4419/Placebo infusion on Day 2.

Table 4 below summarizes the PK sample collection time points. Note that this schedule may be adjusted to accommodate mid/late-week study starts and holidays. Adjustments in the PK schedule must be discussed with the Sponsor or its representative ahead of time. Time of actual blood draws for PK assessment must be recorded in the source notes. Plasma PK samples will be sent to a central laboratory for analysis and interpretation. Further details on PK sample collection, processing, and shipping are provided in a separate manual. Volumes and start/stop times for administration of IV fluids will be collected on PK sampling days.

Table 4: Pharmacokinetic Sampling Schedule to Assess GC4419

Timepoint	Day 1	Day 2	Day 22
Pre-GC4419/Placebo	X	X	X
End of GC4419/Placebo Infusion (+10min)	X		X
Post-IMRT (+10min)	X		X
60-180 min Post End of GC4419/Placebo Infusion	X		X

Galera Therapeutics, Inc.

Version: Amendment 4

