### 10.8. Screening

The following screening observations and procedures will be completed within 28 days of IMRT and GC4419/Placebo start:

Galera Therapeutics, Inc.

Version: Amendment 4

Obtain a signed IRB/IEC/REB-approved informed consent form (ICF)

Confirm subject eligibility by reviewing inclusion/exclusion criteria

Obtain medical history, tobacco use history, and alcohol use history

Obtain HNC history; HNC history should include:

- Tumor HPV status, and strain(s) if known
- Pre-treatment tumor imaging (See Section 10.6.2.1)
- Prior treatments
- Confirmation of histopathological diagnosis of SCC
- Tumor staging (AJCC 8th Edition) (pre-surgical staging for surgical subjects if available; otherwise, provide post-surgical staging)

Conduct a complete physical examination, including height

Ensure a dental examination was conducted for IMRT clearance and potential sources of mucosal irritation (e.g., tooth extraction) were eliminated. The dental exam must occur within the 28-day screening period. The exam must be performed by a licensed clinician, but not necessarily by a dentist. For edentulous subjects, the subject must be cleared for IMRT per SOC (i.e., oral exam).

Conduct OM assessment and record the WHO score

Record planned IMRT and chemotherapy parameters

Measure vital signs, body weight, and ECOG Performance Status

Conduct a 12-lead ECG

Record concomitant medications from date of randomization

Record AEs from date of randomization

Record/update medical conditions and illnesses that have occurred since the subject signed the ICF and record in medical history

Draw blood for laboratory measurements

- Chemistry profile
- Hematology profile
- Biomarker sample for pro-inflammatory cytokine analysis (See Section 10.5)
- For subjects who consent separately: RNA sample (PAXgene) for genomic studies (See Section 10.5)
- Serum pregnancy test for women of childbearing potential

All questions related to subject eligibility should be directed to Galera's Medical Monitor or designee.

Galera Therapeutics, Inc.

Version: Amendment 4

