#### 10.9. Treatment

# 10.9.1. Baseline/Day 1 (First Day of IMRT and GC4419/Placebo)

Prior to receiving the first dose of GC4419/Placebo the following observations and procedures will be conducted for all subjects:

Confirm continued subject eligibility by reviewing inclusion/exclusion criteria

Measure vital signs, body weight, and ECOG Performance Status

Blood pressure must be measured within 30 minutes prior to pre-GC4419/Placebo Infusion PK blood draw (See Section 10.1.1)

Record BSA (used to confirm cisplatin dosing)

Ensure concomitant medications have been recorded from date of randomization

Ensure AEs have been recorded from date of randomization

Record/update medical conditions and illnesses that have occurred since the subject signed the ICF and record in medical history.

Record tobacco use

Conduct first OM assessment for the week and record the severity using the WHO score Draw blood for laboratory measurements

- Chemistry profile
- Hematology profile
- Cotinine test
- PK sampling (See Section 10.4)
- Biomarker sample for pro-inflammatory cytokine analysis (See Section 10.5)

Administer the first GC4419/Placebo dose by continuous intravenous infusion over 60 minutes.

Following GC4419/Placebo administration the following observations and procedures will be conducted for all subjects:

Measure blood pressure prior to End of GC4419/Placebo Infusion PK draw (See Section 10.1.1)

Draw blood for PK sampling (See Section 10.4)

Administer IMRT as soon as possible but no later than 60 minutes following the end of GC4419/Placebo dosing.

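### The only scheduled pregnancy test is at Screening, up to 28 days before the first dose; neither Day 1 nor any later visit schedules another

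*Combined protocol and SAP*

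**What the plan says.** In Appendix 1, the Table 6 row "Blood draw: Serum pregnancy test" has a single mark, in the Screening column. Footnote 14 agrees: "For a woman of childbearing potential, serum pregnancy test must be performed at the Screening Visit". Section 10.8 sets the window: "The following screening observations and procedures will be completed within 28 days of IMRT and GC4419/Placebo start". Section 10.1.2 says that the test is required for women of childbearing potential but names no visit, whereas for cotinine, in the same list, it names three.

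For Day 1, Section 10.9.1 asks staff to "Confirm continued subject eligibility by reviewing inclusion/exclusion criteria". Its blood list covers chemistry, hematology, cotinine, PK and cytokines. Inclusion 8 asks for a negative serum test and sets no time limit of its own. Exclusion 13 separately bars "Female patients who are pregnant or breastfeeding".

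Contraception is covered by Inclusion 9, which begins "Males and females must agree to use effective contraception starting prior to the first day of treatment" and, for women, runs to 30 days after the last dose. Section 11.8 adds that a barrier method should be used for the whole study and the same 30 days, and states that the risks of GC4419 in pregnancy are unevaluated. Section 7.6 lists a confirmed positive serum test among the reasons for stopping study treatment. Section 11.8.1 asks for reports of pregnancies from first dose to 30 days after the last dose.

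**The concern.** A woman who conceives after the Screening test still meets Inclusion 8 on Day 1, because the only result on file is negative. Exclusion 13 obliges staff to consider her current status, but reviewing criteria without a test will not reliably find an early, unrecognised pregnancy. Once dosing starts, the rule in Section 7.6 and the report in Section 11.8.1 both depend on someone finding the pregnancy, and the schedule contains no test that would do so.

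The exposure that the trial adds is GC4419; cisplatin and IMRT are the subject's planned standard care. What is at stake is subject safety. The efficacy inference is not touched.

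The schedule already treats other Screening results as needing renewal. Chemistry and hematology are repeated on Day 1, again on Day 3, 4 or 5, and weekly after that (Table 6, footnote 15).

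**Working it through.** The plan states no figure to reproduce. The check is a search for every scheduled test, followed by day counts.

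1. **Scheduled tests.** Screening (Section 10.8; Table 6, footnote 14): one. Day 1 (Section 10.9.1): none. Day 2 to Last Day of IMRT or early termination (Sections 10.9.2 to 10.9.10): none. Follow-up (Section 10.10): none. Total after Screening: 0.

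2. **Age of the result at first dose.** At most 28 days, the limit of the screening window.

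3. **Age at the last dose of a full course.** Footnote 21 says "GC4419/Placebo will be administered up to 35 times: weekly, Monday through Friday". Thirty-five uninterrupted weekday doses end on Day 47 with a Monday start (as in Table 3) and on Day 49 with a Tuesday to Friday start. Section 10.4.1 expects such starts: "Note that this schedule may be adjusted to accommodate mid/late-week study starts and holidays".
   - Monday start: 28 + (47 − 1) = 74 days.
   - Tuesday to Friday start: 28 + (49 − 1) = 76 days.

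4. **Shorter courses.** Eligible plans deliver 60 to 72 Gy in fractions of 2.0 to 2.2 Gy. The fewest fractions is 60 / 2.2 = 27.3, so 28. The most is 72 / 2.0 = 36, above the cap of 35 doses. A compliant course therefore has 28 to 35 doses. Twenty-eight uninterrupted doses end on Day 38 (Monday to Wednesday start) or Day 40 (Thursday or Friday start), which gives 28 + 37 = 65 or 28 + 39 = 67 days.

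5. **With a test on Day 1.** The result is 0 days old at first dose. The longest gap to the 35th dose falls to 47 − 1 = 46 or 49 − 1 = 48 days. If the sample is instead drawn 3 days earlier (an assumption), each of these figures rises by 3.

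6. **With an optional Week 4 assay as well.** Week 4 is Days 22 to 28. The last Week 4 dosing day is Day 26 (Monday start) or Day 28 (other starts). For a 35-dose course, the longest untested stretch during dosing is:
   - Monday start: the larger of 26 − 1 and 47 − 22, both 25 days.
   - Other starts: the larger of 28 − 1 and 49 − 22, both 27 days.

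7. **Infusions averted.** A positive pre-dose test averts the whole course, up to 35 infusions. At Week 4, 15 doses have been given before the first dosing day of the week and 19 before the last.
   - 35-dose course: 35 − 19 = 16 to 35 − 15 = 20 remain.
   - 28-dose course: 28 − 19 = 9 to 28 − 15 = 13 remain.
   - Overall: about 9 to 20, less any given before the result is back.

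8. **Share that is active drug.** With 3:2 randomisation, 270 / 450 = 60% of subjects receive GC4419.

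All day counts assume no break in IMRT; a break lengthens them.

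**The case against.** The strongest reply is that the protocol already manages pregnancy risk. Contraception is required from before Day 1 through dosing and for 30 days after. Adverse events are recorded on every IMRT day, and subjects' verbal reports are a listed source (Section 11.4). Investigators may test off schedule, and Sections 7.6 and 11.8.1 say what follows if a pregnancy is found. All of this stands, and it lowers the risk. It is weakest for the interval between Screening and Day 1: Inclusion 9 does not say how long before treatment contraception must begin. Detection through symptoms may also be poor, because Section 9.2.1 classes cisplatin as highly emetogenic and nausea could be put down to it; that is an inference, not a statement in the plan.

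The benefit cannot be expressed as an expected number of pregnancies, since the documents do not give the number of women of childbearing potential. This also stands. So does the point that a change means a further amendment to a trial enrolling since October 2018 at about 100 sites.

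A reader might infer that the protocol contradicts itself, or knowingly admits pregnant women. It does neither: Exclusion 13 applies on Day 1, and what is missing is the test that would make it dependable. A reader might also infer that no visit could reveal a pregnancy. The documents support only the narrower statement that no test is scheduled; a subject may report one at any visit.

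**Conclusion.** The gap is real. One scheduled test, up to 28 days old at first dose, covers a dosing period at whose end the result is up to 74 to 76 days old for an uninterrupted 35-dose course (65 to 67 days for the shortest compliant course). A repeat test before the first infusion is a cheap safety improvement and should be made. A Week 4 assay is secondary: contraception is required throughout that period, and fewer infusions remain to avert.

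Two stronger readings of the size should be avoided. Averting up to 35 infusions is not averting 35 doses of GC4419 in every case, because about 40% of subjects receive placebo. Nor does every Week 4 positive leave 16 to 20 infusions; that range holds only for a 35-dose course, and 9 to 20 covers the compliant range. The number of women affected is unknown and may be small. Alpha, power and the primary analysis are unaffected.

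**What to change.** In Table 6, footnote 14 and Section 10.9.1, require a repeat pregnancy test for women of childbearing potential, with a negative result available before the first infusion. Allow either of two routes:

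- a local test on Day 1, stated as an exception to the central-laboratory rule in Section 10.1.2; or
- a central-laboratory sample a few days before Day 1.

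Optionally, add one pregnancy assay to the existing Week 4 safety draw.

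The cost is one routine assay per woman of childbearing potential, or two with Week 4. A local kit, an earlier draw or an extra tube may be needed; sample volumes are not given. The change also needs a protocol amendment and IRB/IEC/REB approval before use (Section 14.4).
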